6.2. Safety Endpoints

Treatment-emergent adverse events (TEAE) are defined as any event increasing in severity from baseline or any new event starting during bosutinib therapy or within 28 days of the last dose of study drug (using 28 day lag).

6.2.1. Exposure and Compliance

Exposure and compliance data will be collected during this study. The primary exposure endpoints while the patient is on treatment are duration of treatment, cumulative dose received, dose over time, reasons for dose modifications (reduction, delay, or escalation), and reasons for treatment discontinuation. Duration of treatment is the time from first non-zero dose to last non-zero dose ([date of last non-zero dose – first dose date +1]/30.4). Planned dose is 500 mg/day.

6.2.2. Laboratory Evaluations, Vital Signs, and Cardiac Evaluations

Laboratory values, electrocardiogram (ECG) data, and left ventricular ejection fraction (LVEF) data from echocardiogram (ECHO) or multiple gated acquisition (MUGA) scans will be collected during this study from local laboratories. Collection time points for these measurements are specified in the protocol. Laboratory values and LVEF data will be graded according to NCI CTC version 4.03. ECG assessments (time intervals) will be graded as Normal: <450, Grade 1: ≥ 450 -480, Grade 2: >480-500, and Grade 3: >500 milliseconds.

If multiple post-baseline observations occur at the same visit, the most serious (highest grade) evaluation will be used for all summaries.

6.2.3. Laboratory Evaluations of Special Interest

Laboratory parameters including but not limited to alanine aminotransferase (ALT), aspartate aminotransferase (AST), serum creatinine, estimated glomerular filtration rate (eGFR), platelets, neutrophils, WBC, and hemoglobin will be summarized. Endpoints include distribution of maximum toxicity, time to first event (time from first dose to date of first event including only non-partial dates), duration of any grade event (time from start date to stop date including only non-partial dates), and cumulative duration of grade 3b/4/5 events for eGFR and grade 3/4 events for others (sum of time from start dates to stop dates including only non-partial dates for all events).

eGFR will be derived based on the Modification of Diet in Renal Disease (MDRD) study formula: $175 \times \text{SerumCreatinine}^{-1.154} \times \text{age}^{-0.203} \times 1.212$ (if patient is black) $\times 0.742$ (if female), creatinine measured in mg/dL. eGFR will be graded according to the Kidney Disease Improving Global Outcomes (KDIGO) Kidney function stages (Grade 1: ≥ 90 , Grade 2: $60 < 90$, Grade 3a: $45 < 60$, Grade 3b: $30 < 45$, Grade 4: $15 < 30$, and Grade 5: $< 15 \text{ mL/min/1.73 m}^2$).

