- Treatment with bosutinib may result in a clinically significant decline in renal function in CML patients. A decline over time in estimated glomerular filtration rate (eGFR) has been observed in CML patients with bosutinib treatment. It is important that renal function is assessed prior to bosutinib treatment and closely monitored during therapy, with particular attention in those patients who have preexisting renal compromise or in those patients exhibiting risk factors for renal dysfunction, including concomitant use of medicinal products with potential for nephrotoxicity such as diuretics, angiotensin converting enzyme (ACE) inhibitors, angiotensin receptor blockers and nonsteroidal anti-inflammatory drugs (NSAIDs). Bosutinib exposures were increased in patients with moderately and severely impaired renal function. Dose reduction is recommended for patients with moderate or severe renal impairment.

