8.2.4.4. Laboratory Evaluations of Special Interest

The number and percentage of maximum on-treatment grade 0 through 4 for serum creatinine, ALT, AST, platelets, neutrophils, WBC, and hemoglobin and grade 1 through 5 for eGFR will be summarized. Descriptive statistics for time to first event, duration of any grade event, and cumulative duration of grade 3b/4/5 for eGFR and grade 3/4 events for others will be calculated. Shifts from baseline to maximum on-treatment grade will also be presented.

A listing will be provided for patients who potentially meet the Hy's law criteria. Potential is defined as meeting these 3 criteria any time during the study (non-concurrent): AST or ALT level of $\geq 3 \times$ upper limit of normal (ULN), total bilirubin level of $> 2 \times$ ULN, and alkaline phosphatase level $< 2 \times$ ULN. Total Bilirubin, AST, ALT, and alkaline phosphatase will be listed.

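### eGFR is graded on a scale with no normal category, so, read literally, its time to first event and any-grade duration say nothing about renal toxicity

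*SAP*

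**What the plan says.** SAP section 6.2.3 names eGFR in one list with ALT, AST, serum creatinine, platelets, neutrophils, WBC and hemoglobin, and gives the whole list the same endpoints. Two matter here: "time to first event (time from first dose to date of first event including only non-partial dates), duration of any grade event". The second is counted between the dates on which the event starts and stops, again with complete dates only.

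A third endpoint has a threshold of its own for eGFR: "cumulative duration of grade 3b/4/5 events for eGFR and grade 3/4 events for others".

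On the scale, the section says "eGFR will be graded according to the Kidney Disease Improving Global Outcomes (KDIGO) Kidney function stages". The bands are Grade 1 at 90 or more, Grade 2 from 60 to below 90, 3a from 45 to below 60, 3b from 30 to below 45, Grade 4 from 15 to below 30, and Grade 5 below 15.

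SAP section 8.2.4.4 repeats these statistics and shows the difference in scale. For the other parameters it plans "The number and percentage of maximum on-treatment grade 0 through 4 for serum creatinine" and the rest of that list, while "grade 1 through 5 for eGFR will be summarized". It also plans shifts from baseline to maximum on-treatment grade.

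The only baseline-relative event rule is in SAP section 6.2. It defines treatment-emergent adverse events and does not mention laboratory events.

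**The concern.** An any-grade rule works only if the scale has a grade meaning no event. The toxicity grades have one, grade 0. The KDIGO stages as written do not, so a patient with normal filtration is Grade 1 and counts under an any-grade rule.

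The authors evidently saw that eGFR needs separate handling, since they set a 3b/4/5 threshold for cumulative duration. They did not carry a threshold over to the other two statistics. For ECG intervals, SAP section 6.2.2 writes out a normal category; eGFR has no counterpart.

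Renal function is a named risk. Protocol section 4.3 states: "A decline over time in estimated glomerular filtration rate (eGFR) has been observed in CML patients with bosutinib treatment". Time to first event and event duration are the natural summaries of when such a decline starts and how long it lasts. If both return the same answer whatever the kidneys do, that part of the renal time course is lost, or it rests on a definition chosen at the programming stage.

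**Working it through.** **1. Does any eGFR value escape a grade?** The six bands meet without gaps and cover every positive value, so the lowest possible grade is 1. The SAP's MDRD formula is eGFR = 175 × creatinine^-1.154 × age^-0.203, × 0.742 if female and × 1.212 if Black. Example values, non-Black patients:

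| Patient | Creatinine (mg/dL) | eGFR | Grade |
|---|---|---|---|
| Man, 60 | 0.8 | 175 × 1.294 × 0.4355 = 98.6 | 1 |
| Man, 40 | 0.9 | 93.5 | 1 |
| Woman, 60 | 0.7 | 85.4 | 2 |
| Man, 65 | 1.3 | 55.4 | 3a |
| Man, 65 | 1.8 | 38.1 | 3b |

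All five have an any-grade event, including the two with normal filtration.

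**2. When does the literal event start?** SAP section 6 treats Week 1 Day 1 samples as pre-dose. Protocol section 6.2 schedules the next chemistry panel at Week 1 Day 7 (± 1 day). If any graded value is an event, every patient with an on-treatment creatinine has the first event at that sample.

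**3. How long does it last?** No value is ungraded, so none ends the event. A patient sampled from Day 7 to Week 208 has a duration of 208 × 7 − 7 = 1,449 days. One whose last sample is at Week 26 has 26 × 7 − 7 = 175 days. The statistic measures time under observation, and a patient who stops early has a shorter event whatever the eGFR.

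**4. What would other definitions give?** This is an illustrative simulation on the protocol visit schedule. Every input is an assumption, not a document figure: mean baseline eGFR 75, 85 or 95; between-patient SD 20; true baseline at least 45; within-patient SD 7; slope −2 or −5 per year; no dropout. Ranges are over the six scenarios.

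| Event definition | Patients with an event, ever | Event at Day 7 |
|---|---|---|
| Any grade (literal) | 100% | 100% |
| Grade 2 or worse | 70–97% | 40–75% |
| Stage worse than own baseline | 44–84% | 9–14% |
| New 3b or worse | 4–32% | 0.3–2% |

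The literal definition gives 100% at both slopes. At mean baseline 85, going from −2 to −5 per year moves worse-than-baseline from 52.1% to 78.0%, and new 3b or worse from 8.6% to 19.9%. Those two definitions respond to the size of the decline. Dropping Grade 1 alone is not enough, because many patients start in Grade 2.

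**5. Other parameters.** These have a grade 0, so the scale problem does not arise. The SAP still does not require a laboratory event to be worse than baseline. Protocol section 4.1 admits fourth-line CP and AP/BP patients with neutrophils just above 0.5 × 10^9/L and platelets of 50 × 10^9/L. A footnote to Table 4 in Protocol section 5.2.2 expects some AP/BP patients to enter with Grade 3 neutropenia or anemia from their disease. Read literally, such a cytopenia, if still present at Day 7, is an on-treatment event. The documents do not give the proportion of patients affected.

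**The case against.** The strongest reply is that the literal result is not what the SAP orders. Any grade qualifies only the duration statistic. For time to first event the text says nothing about which grade counts, and a programmer might borrow the treatment-emergent rule from SAP section 6.2, which heads the same part of the document. The first half of this stands: for time to first event the defect is an undefined term. The second half does not cure it, because that rule is written for adverse events and is nowhere extended to laboratory values. For duration, the any-grade wording is explicit.

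A reader might also infer that renal decline could not be told from normal function, or that all the planned eGFR time and duration output is empty. The documents do not support either. Section 8.2.4.4 plans maximum eGFR grade and shifts from baseline. Cumulative duration of 3b/4/5 has a proper threshold. Serum creatinine is graded from 0 and has its own time-to-first-event and duration summaries. Renal toxicity is an adverse event of special interest in SAP sections 6.2.8 and 8.2.4.9, although its definition is left until before database lock. Protocol section 9.4 plans descriptive statistics of laboratory change over time.

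Finally, any replacement definition involves judgement, and a single value near a stage boundary can cross by noise. That stands. In the simulation the steepest slope produces a true fall of only 5 × 7/364 = 0.1 mL/min/1.73 m2 by Day 7, so the 9–14% flagged then as worse than baseline is almost all noise. It is a reason to show new 3b or worse alongside.

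**Conclusion.** The point holds for two eGFR summaries. Any-grade duration, as worded, is uninformative because the scale has no grade below 1. Time to first event is undefined, and on the literal reading it is uninformative too: 100% of patients with an on-treatment creatinine have an event at the first post-dose sample. The 100% follows from the bands and needs no assumption about renal function. It does depend on counting any graded value as an event, which for time to first event the SAP neither says nor rules out. The percentages under other definitions rest on the assumed simulation inputs and show direction only.

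The consequence is limited to descriptive safety tables in a single-arm study without hypothesis tests. No primary or secondary efficacy result changes, and other planned renal summaries remain usable. It is worth correcting because renal decline is a named risk and the correction is cheap. The lack of a baseline-relative rule for the other laboratory parameters is a secondary point of unquantified size.

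**What to change.** In SAP sections 6.2.3 and 8.2.4.4:

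- For time to first event and duration, define the eGFR event as the first on-treatment value in a KDIGO stage worse than the baseline stage. End the event on return to the baseline stage, and state how an event still open at the last sample is handled.
- Report alongside it the first on-treatment value in stage 3b or worse among patients above 3b at baseline (eGFR 45 or more). This is less exposed to boundary crossings by measurement noise.
- Keep the maximum-grade, shift and cumulative 3b/4/5 duration summaries as planned.
- As a secondary change, state that a laboratory event for the other parameters must be a grade worse than baseline, in line with the treatment-emergent rule in SAP section 6.2.

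The cost is a few sentences and a programming change. Baseline and on-treatment values are already collected. The small downside is that the worse-than-baseline summary will include some crossings due to noise, which is why both eGFR summaries should be shown.

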6.2.8. Adverse Events of Special Interest

Adverse events including ALT, AST, thrombocytopenia (including MedDRA preferred term [PT] Platelet Count Decreased), neutropenia (including PT Neutrophil Count Decreased), leukopenia (including PT White Blood Cell Count Decreased), anemia (including PT Hemoglobin Decreased), diarrhea, nausea, vomiting, cardiac toxicity (definition to be determined before DBL), vascular toxicity (definition to be determined before DBL), and renal toxicity (definition to be determined before DBL) will be summarized. Additional AEs or AE clusters may be summarized if deemed appropriate. AE characteristics to be

summarized include maximum toxicity, time to first event, duration of any grade event, cumulative duration of grade 3/4 events, and successful rechallenge (those patients who were re-dosed and did not discontinue bosutinib due to this AE after having a dose delay).

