8. STATISTICAL METHODOLOGY AND STATISTICAL ANALYSES

8.1. Statistical Methods

8.1.1. Analyses of Continuous Data

For continuous variables, the descriptive statistics include n, mean, median, standard deviation (SD), and range (minimum, maximum).

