8.2.4.9. Adverse Events of Special Interest

The number and percentage of maximum treatment-emergent CTCAE grade events and successful rechallenge for ALT, AST, thrombocytopenia (including MedDRA PT Platelet Count Decreased), neutropenia (including PT Neutrophil Count Decreased), leukopenia (including PT White Blood Cell Count Decreased), anemia (including PT Hemoglobin Decreased), diarrhea, nausea, vomiting, cardiac toxicity, vascular toxicity, and renal toxicity will be summarized. Descriptive statistics for time to first event, duration of any grade event, and cumulative duration of grade 3/4 events will be calculated for selected parameters.

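### SAP 6.2.3 measures laboratory event duration from start to stop date only, so unresolved events contribute nothing and durations and cumulative time come out too short

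*SAP*

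**What the plan says.** **Laboratory events.** SAP 6.2.3 sets the endpoint as "duration of any grade event (time from start date to stop date including only non-partial dates". Cumulative duration (grade 3b/4/5 for eGFR, grade 3/4 for the other parameters) is the "sum of time from start dates to stop dates including only non-partial dates for all events". SAP 8.2.4.4 then plans "Descriptive statistics for time to first event, duration of any grade event, and cumulative duration of grade 3b/4/5 for eGFR", with grade 3/4 for the rest. SAP 8.1.1 says what that means for a continuous variable: "the descriptive statistics include n, mean, median, standard deviation (SD), and range (minimum, maximum".

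**Adverse events of special interest.** SAP 6.2.8 lists "time to first event, duration of any grade event, cumulative duration of grade 3/4 events, and successful rechallenge" but gives no formula for any duration. SAP 8.2.4.9 again plans descriptive statistics only: "duration of any grade event, and cumulative duration of grade 3/4 events will be calculated for selected parameters".

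**Missing data.** SAP Section 7 rules out imputation in general. Its partial-date rule needs at least a year, so it cannot supply a date that is wholly absent. Its censoring rule lists time to response, duration of response, time to transformation, PFS and OS, and refers to Section 6.1. Safety durations are not listed there, nor among the endpoints of SAP 8.1.4.

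**Observation after treatment.** The Schedule of Activities (Protocol Table 1) has no laboratory tests in the follow-up column, and Protocol 6.4 limits that phase essentially to survival status. For adverse events, Protocol 8.1.4.1 and 8.1.4.2 provide for investigator follow-up until the event resolves or stabilises.

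**The concern.** A laboratory abnormality still present at the last assessment has a start date and no stop date. The formula in SAP 6.2.3 cannot give it a value, and no other section does so. The summary is then taken over resolved events alone. Long events are the ones most likely to outlast observation, so the selection favours short ones.

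This matters most for toxicity that does not go away. Protocol 4.3 states: "A decline over time in estimated glomerular filtration rate (eGFR) has been observed in CML patients with bosutinib treatment". Under the cumulative rule, a patient who reaches grade 3b eGFR and stays there until the end of treatment adds no time, while a patient who recovers does add time. The durations are meant to describe how long toxicity lasts, in a study whose stated purpose is to supply further safety and efficacy data in support of full marketing authorisation.

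**Working it through.** The plan gives no duration, resolution rate or share of ongoing events, so there is no figure to reproduce. The check has two parts.

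**1. Does any rule pick up an unresolved laboratory event?**
- Duration formula (SAP 6.2.3): needs a complete stop date. No value.
- Cumulative formula (SAP 6.2.3): a sum of the same intervals. Adds zero.
- Imputation (SAP 7): none in general; partial dates only. No stop date supplied.
- Censoring (SAP 7, 8.1.4): efficacy endpoints only. Does not apply.
- Summary (SAP 8.2.4.4 with 8.1.1): n, mean, median, SD, range. No censoring method.
- Later data (Protocol Table 1, 6.4): no scheduled laboratory test after End of Treatment that could close the event.

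SAP 8.2.2 also notes that more than 80% of patients were off treatment by 11 March 2020, so most laboratory series had ended by then.

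**2. Direction and illustrative size.**

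Assumptions, none from the documents: event duration D is exponential with mean m; follow-up after onset C is uniform on 0 to T months; D and C are independent.

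An event of length d (up to T) is seen to resolve with probability 1 − d/T. This falls as d rises, which gives the direction of the bias.

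Share unresolved = (m/T)(1 − e^(−T/m)). For m = 12 months, the true median is 12 × ln 2 = 8.3.
- T = 24: 0.5 × (1 − e^(−2)) = 0.432
- T = 48: 0.25 × (1 − e^(−4)) = 0.245

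The resolved-only median is the midpoint of the density proportional to e^(−d/m)(1 − d/T). The cumulative share is the time in resolved events divided by all event time observed.

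| True median (months) | T (months) | Events dropped | Resolved-only median (months) | Share of observed event time counted |
|---|---|---|---|---|
| 2.1 (m = 3) | 24 | 12% | 1.8 | 86% |
| 2.1 | 48 | 6% | 1.9 | 93% |
| 8.3 (m = 12) | 24 | 43% | 4.5 | 48% |
| 8.3 | 48 | 25% | 6.1 | 70% |
| 16.6 (m = 24) | 24 | 63% | 5.6 | 28% |
| 16.6 | 48 | 43% | 8.9 | 48% |

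**Does censoring repair it?** A separate simulation took onset as uniform over a 24-month window, with observation continuing 28 days beyond it and exponential durations. A true median of 12 months gave a resolved-only median of 5.26 and a Kaplan-Meier median of 11.96. With a true median of 48 months, Kaplan-Meier correctly showed the median as not reached, while the resolved-only rule still reported 6.73 months.

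**The case against.** **The SAP does not say that unresolved events are excluded.** This is true. A reader might infer an explicit exclusion rule, and there is none. The words about non-partial dates deal with incomplete dates, and the SAP does not say how a stop date is derived from serial laboratory values. If the programmer took the last abnormal value as the stop, ongoing events would stay in, cut short. The drop-out shares above would then not apply, but the bias would keep its direction. Under the same assumptions the median of min(D, C) solves e^(−x/12)(1 − x/T) = 0.5, which gives 5.3 months (T = 24) or 6.6 months (T = 48) against a true 8.3.

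**Adverse events are not shown to be affected.** A reader might infer that adverse event durations share the defect on equal footing. The documents do not support that. The formula is written for laboratory parameters only, and follow-up to resolution or stabilisation may supply late stop dates. What stands is that a stabilised but unresolved event still has no stop date and no rule.

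**The renal example can be pushed too far.** One might infer that renal decline is the most distorted endpoint, or that all eGFR durations are. Protocol 4.3 reports a decline but gives no duration or recovery rate. SAP 6.2.3 puts eGFR grade 1 at 90 or above, so every value has a grade and an any-grade eGFR duration has no clear start or stop. The point applies to sustained grade 3b or worse.

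**The consequence is limited.** The study is single-arm with no hypotheses. Maximum grade and shifts from baseline (SAP 8.2.4.4) and adverse event incidence (SAP 8.2.4.8) do not need a stop date, so an unresolved eGFR decline remains visible there. This stands. It limits the reach of the error but does not make the durations right.

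**Kaplan-Meier is not automatically unbiased.** Stopping bosutinib for toxicity can make the censoring informative, and both calculations assume that it is not. This also stands, and is why the number unresolved must be reported beside any median.

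**Conclusion.** The concern holds for laboratory events. Followed as written, SAP 6.2.3 gives an unresolved event no duration and no cumulative time, and SAP Section 7 does not rescue it. The reported figures are therefore biased short, more so the longer the toxicity lasts. For adverse events (SAP 6.2.8, 8.2.4.9) the same outcome is an inference from identical endpoint names and a descriptive-only analysis.

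The direction rests on little more than the end of observation being unrelated to event length. The size is not known. The illustrative figures depend wholly on the exponential and uniform assumptions and are not estimates for this trial. They show that events with a median of about 2 months are hardly affected, while a true median of 8.3 months could be reported as about 4.5 to 6.1. No efficacy result and no incidence, grade or shift table changes. This should be corrected, but it does not put the study's overall safety assessment in doubt.

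**What to change.** In SAP 6.2.3 and 8.2.4.4, and likewise in 6.2.8 and 8.2.4.9:
- State how a laboratory event's stop date is derived, and give the adverse event duration formula.
- Keep ongoing events, and report the number and percentage unresolved.
- In cumulative duration, count the observed time of ongoing events up to the last available assessment.
- Report a Kaplan-Meier median duration, censoring unresolved events at the last assessment of that event. For laboratory events this is the last on-treatment value within 28 days of last dose, the window already in SAP Section 6. For adverse events it is the last adverse event follow-up date, keeping any later recorded resolution date.
- Note that censoring at discontinuation for toxicity may be informative.
- Limit eGFR durations to grade 3b or worse.
- Reconcile the restriction to non-partial dates with the partial-date imputation in SAP Section 7.

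No new data are needed. The cost is SAP wording and slightly more programming. Reported durations will become longer, and some medians may be shown as not reached.
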